The study to be Carried out will be Explained and read and, where appropriate, the informed consent will be signed by the Patient During the initial visit (Visit 1) of eligibility, Where the subject will be Given 2 questionnaires (see annexes), one They meet to determine if the ROME III criteria for functional constipation (FC) and another to ASSESS if the patient does not meet the criteria for irritable ROME III bowel syndrome (IBS) and a baseline breath test will be performed.

Having met the inclusion criteria, the patient will be EVALUATED by a graduate in nutrition with the objective of Evaluating the fiber intake in the subject's usual diet. The amount of daily fiber intake will be standardized and a diary will be Given to Evaluate Said intake (see annexes) as well as a diary Where the subject will keep a record of his / her evacuations (see annexes).

In Addition, the previous use of fiber supplements and laxatives, which must be suspended at Least 2 months prior to randomization, will be EVALUATED.

The subject will return to a second visit (Visit 2) (Which will depend on Whether the patient is taking laxatives or fiber supplements) for a complete physical evaluation and the fiber intake diary will be Assessed to determine the amount of fiber intake in the diet as well as the diary of evacuations and the SmartPill © will be Given and That way, the patient will return to the hospital to register the data after the capsule Having evacuated.

The patient will return a week later (Visit 3) on a 12 hour fast, the fiber intake and the evacuation diaries will be re-EVALUATED and will be EVALUATED They again by a nutritionist. A new breath test will be Carried out. The subject will be

Asked to complete the SF-36 Quality of Life Questionnaire. A stool sample will be Collected for ITS analysis in Addition to a blood sample for determination of fasting glucose, glycosylated hemoglobin A1c, Insulin and full lipid profile.

The subjects will be randomized to receive one of four treatments That can be Psyllium plantago 15g, blue agave Tequilana Weber fructans at doses of 5, 10g and blue agave Tequilana Weber fructans at a dose of 5 g + 10 g excipient for a concentration of 33 % of blue agave fructans Tequilana Weber.

The randomization will be computer-generated with a participation number and the assignment of the treatment will be consecutive.

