The product will be supplied in identical bottles With the same amount of powder in a container That will only be identifiable With the name of the protocol as well as the patient's number.

The patient will be provided with a measuring spoon to administer the amount of product Necessary for each of the doses (5, 10 and 15g respectively) or with envelopes Containing the exact Amounts Weighed.

The patient will be instructed to keep a diary of the diet, of the evacuations and a sheet to ASSESS adverse effects. The subject will return (Visit 4) at the end of a month \pm 5 days on a 12 hour fast and Their adherence will be Assessed by product weight in the container subtracting the number of grams required daily ACCORDING TO the assignment of treatment.

The fiber intake diaries will be EVALUATED again by the nutritionist, the evacuation will Also be EVALUATED diary. A medical evaluation will be Carried out That includes questioning and physical evaluation. Subsequently, a blood sample will be to determine fasting glucose Obtained, glycosylated hemoglobin A1c, insulin and lipid profile and a full sample of excrement will be Obtained and SmartPill® will be Given.

The patient will Continue with the supplement in the same container and will be scheduled for a month later. In the end-of-treatment visit visit (visit 5), the fiber will be EVALUATED journals consumption again by a nutritionist and the evacuation will be EVALUATED diary as well.

A medical evaluation will be Carried out That includes questioning and physical evaluation and Their adherence will be Assessed by weighing the product in the container, subtracting the number of grams That it requires daily ACCORDING to the treatment assignment or delivery by the patient of the empty envelopes used.

Subsequently, a blood sample will be to determine fasting glucose Obtained, glycosylated hemoglobin A1c, insulin and lipid profile and a full sample will be Collected stool and breath test at the end will be Carried out.

For end of the visit, Which Will Be Carried out one month after stopping the treatment, the evacuation will be EVALUATED diary and a stool sample will be Collected and with it the intervention in the part of the study will end. Total The follow-up duration for each patient will be 3 months, enough time to observe and compare the effect of the fibers to be used. It is Important to mention That in recent studies Carried out by the same team and with blue agave Tequilana Weber fructans,

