spontaneous evacuation It is defined as an evacuation in the absence of use of laxatives, suppositories or enemas and complete evacuation is defined as spontaneous evacuation to that sensation of incomplete emptying of the rectal ampulla.

secondary measured variables:

- I. Effect of supplementation of fructan Weber blue agave Tequilana in the form of bowel movements, assessed by the Bristol scale. It is defined as a change in the form of evacuations when presenting a change in the classification of Bristol, more than 50% according to the daily evacuations taking the average of the evacuations submitted within 15 days.

- II. Effect of supplementation of fructan Weber blue agave Tequilana in the frequency of bowel movements. It shall be defined as responder presenting increased 50% in stool frequency compared with baseline, according to the daily bowel movements taking the average of evacuations presented at 15 days.
- III. Evaluate the impact of the concentration of short-chain fatty acid, particularly butyrate, in the feces of subjects before and after addition of fructans Tequilana Weber blue agave. The butyrate concentration was determined by method of gas chromatography and the increase will be assessed in millimoles per liter.
- IV. Evaluate the impact of supplementation fructans Weber blue agave Tequilana the microbiota by determining edges present in feces of the subjects before and after the supplementation fructan derivatives fiber; which are:
 - 1) **Actinobacterias** (Bifidobacteriales)
 - 2) **Bacteroidetes** (Prevotella, Paraprevotela, Ruminococcaeaceae, Faecalibacterium)
 - 3) **Firmicutes** (Veillonella, Anaerostipes, lactobacilli Clostridiales, Enterococcus)
 - 4) **Proteobacteria** (Bilophila, Escherichia).
 - 5) **Euryarchaeota** (Methanobacteriales)
- V. To evaluate the impact of serum glucose concentration and HbA1c fasting serum of subjects before and after addition of fructans Tequilana Weber blue agave. HbA1c concentration is determined as it is intended to monitor the impact of fiber on glucose throughout the duration of the study (2 months) and in order to avoid the variability that fasting glucose.

Gas Chromatography: (determination of short-chain fatty acid AGCC)

AGCC for determining ion detector flame will be used. The following steps are performed:

1. ethylbutyrate - 1 g of faeces which is added 50 uL of 2 homogenizará.
2. 1 mL of hydrochloric acid was be added.

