Sequencing and analysis of the amplified fragments is by fluorescent sequencing equipment terminator 3130 / genetic analyzer (Applied Biosystems).

The PCR products were sequenced and analyzed and will be submitted to GenBank for species identification.

Extracting bacterial DNA and quantitation of bacterial species used to demonstrate the prebiotic effect of agave fiber, since selective growth of the population of bifidobacteria and lactobacilli and occurrence of short-chain fatty acid in stool is expected.

Thus in addition to the functional properties and their effects on constipation, you may check the prebiotic effect of agave fructans.

Data analysis:

a) Statistical analysis plan

The data obtained will be analyzed with SPSS version 24. For continuous variables the results are presented in mean ± standard deviation when the variables are normally distributed or medians and percentiles otherwise and as frequency and percentages when they were categorical. For basal and subsequent comparison to the intra intervention groups, Student's t-test for paired samples (variables with normal distribution) or the Mann-Whitney U (variables without normal distribution) is used in the case of continuous variables and X² or the McNemar test in the case of categorical variables. For comparison between groups ANOVA (variables with normal distribution) or Kruskal-Wallis (non-normal distribution variables) used for continuous variables and the same percentage of change obtained when the variables are continuous.

Also an analysis of covariance (ANCOVA) was performed to control variables that might have an effect on the response variables.

b) Non-inferiority study

There are multiple fibers on the market that are promoted as beneficial supplement to patients with constipation; Despite this, there is insufficient scientific evidence from randomized controlled trials to support its use. Psyllium psyllium, is the first-line treatment used for such functional bowel disorder; fructans tequilana Weber blue variety are soluble fibers which are rich fructooligosacáridos role in prebiotic substance with the which is associated with a number of health benefits including intestinal health; therefore, as an alternative treatment in patients with constipation using these fructans it is raised to generate clinical evidence and demonstrate the therapeutic potential similar to plantago psyllium.

c) Sample size

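### For continuous secondary outcomes the plan does not say which between-arm analysis decides, whether baseline is adjusted for, or at which visit; the Bristol response has no direction.

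*Combined protocol and SAP*

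**What the plan says.** **Tests.** Section 10, Data analysis, a) Statistical analysis plan gives paired tests within arms. Between arms it gives ANOVA or Kruskal-Wallis, chosen by distribution, "used for continuous variables and the same percentage of change obtained when the variables are continuous". It then adds that "an analysis of covariance (ANCOVA) was performed to control variables that might have an effect on the response variables". No covariate is listed and no analysis is ranked above another.

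**Outcomes.** The continuous secondary variables are fecal butyrate (item III), microbiota (item IV), and glucose and HbA1c (item V), each described as before and after supplementation. For butyrate, "the increase will be assessed in millimoles per liter".

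**Measurements (section 8, Study Design).**
- Visit 3, before randomization: "A stool sample will be Collected for ITS analysis in Addition to a blood sample for determination of fasting glucose".
- Visit 4, one month: "insulin and lipid profile and a full sample of excrement will be Obtained".
- Visit 5, which the section labels the end of treatment: "insulin and lipid profile and a full sample will be Collected stool and breath test at the end will be Carried out".
- One month after stopping: stool again, and the evacuation diary.

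**Stool form and frequency.** Item I (Bristol) defines an effect as "presenting a change in the classification of Bristol, more than 50% according to the daily evacuations", averaged over 15 days. Item II (frequency) does state a direction: "It shall be defined as responder presenting increased 50% in stool frequency compared with baseline". It also averages over 15 days.

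**The concern.** One outcome can be compared between arms on follow-up values, on change or with covariate adjustment. Blood has two post-baseline readings and stool has three, one of them off treatment. These can give different answers, and the plan does not say which one is the result.

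With 15 patients per arm, chance differences at baseline are common. An unadjusted comparison carries part of them into the estimate, although the data to remove them are already collected.

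The Bristol definition raises a different problem. A response that does not separate softer from harder stool, and sets no upper limit, cannot be read as benefit. The theoretical framework (section 6) itself lists diarrhea among the side effects of agave fructans, so a move to watery stool is foreseeable.

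**Working it through.** **1. What the plan fixes.** The plan prints no figure on this point. Its sample size takes λ/Δ = 10.91/1, rounded to 11, and arrives at 15 per arm after allowing for losses. The value 10.91 agrees with the noncentrality of a four-group test (3 df, alpha 0.05, power 80%), recomputed as 10.90. That is a comparison without a covariate. I take 15 per arm as given.

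**2. Assumptions (not in the documents).** The outcome is normal and in SD units. One of four arms is 1 SD higher. The baseline-to-follow-up correlation is r = 0.3, 0.5 or 0.7. The test is the omnibus test at alpha 0.05.

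**3. Power at 15 per arm.** The arm means are 1, 0, 0, 0 with average 0.25. The sum of squared deviations is 0.75² + 3 × 0.25² = 0.75, so the noncentrality is 15 × 0.75 = 11.25 for follow-up values. The other two analyses divide this by their relative variance:

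| Analysis | Relative variance | Noncentrality, r = 0.3/0.5/0.7 | Power |
|---|---|---|---|
| Follow-up value, unadjusted | 1 | 11.25 throughout | about 78–79% |
| Change score | 2(1 − r) | 8.04/11.25/18.75 | 63/79/95% |
| ANCOVA on baseline | 1 − r² | 12.36/15.00/22.06 | 82/89/98% |

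Power is from simulation; the noncentral F distribution agrees to about 1 point. At r = 0, ANCOVA is about 1 point below the unadjusted test. At 12 per arm (20% loss), unadjusted power is about 67% and ANCOVA about 70/80/93%.

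**4. Do the analyses agree?** Unadjusted ANOVA and ANCOVA fall on opposite sides of p = 0.05 in about 8/14/20% of simulated trials. For change score against ANCOVA the figures are about 24/14/3%.

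**5. Precision.** The 95% CI half-width for one agave arm minus psyllium is 2.003 × √(2/15) = 0.73 SD unadjusted. With baseline adjustment it is 0.70/0.64/0.53 SD.

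**6. Baseline imbalance.** The standard error of a baseline difference is √(2/15) = 0.365 SD. The chance that a given agave arm starts more than 0.5 SD from psyllium is 17%; for at least one of the three it is 38%. At a 0.5 SD imbalance the unadjusted difference is off on average by 0.5r = 0.15/0.25/0.35 SD. A change score is off by 0.5(1 − r) = 0.35/0.25/0.15 SD in the opposite direction.

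**7. Bristol.** Assume the usual 1 (hardest) to 7 (most liquid) scoring, which the documents do not print, and read 50% as a ratio of mean scores:
- 3 to 1 is (1 − 3)/3 = −67% and counts.
- 2 to 7 is (7 − 2)/2 = +250% and counts.
- 2 to 3 is exactly +50% and does not count as more than 50%.

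A softer move qualifies from a baseline mean below 7/1.5 = 4.67, a harder move from one above 1/0.5 = 2. Between those values both directions can qualify.

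**The case against.** **Between-arm tests are named.** A reader might infer that the plan has no between-arm analysis. It has; what is missing is a ranking and a covariate.

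**Butyrate.** The increase in mmol/L implies a change score, which already uses baseline. This stands. At r = 0.7 it has 95% power against 98% for ANCOVA, and the two disagree in only about 3% of trials. The gain of roughly 20 points over unadjusted values therefore should not be applied to butyrate. At r = 0.3 the change score is the weakest of the three.

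**The visit can be guessed.** Objective 4 compares butyrate before and after treatment, section 8 labels Visit 5 the end of treatment, and item V mentions two months. These cues favor Visit 5. None of them sets an analysis visit.

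**Inflated false positives.** A reader might infer that success will be claimed on whichever analysis is significant. The plan states no such rule, so no error rate is attached here. Likewise, the translated sentence does not show whether percent change is tested between arms or only calculated.

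**Bristol.** The 50% may mean a share of stools rather than a score ratio; the ratio figures would then fall away. Even as a ratio, seven of the nine harder moves between whole types start from types 5–7, unlikely baselines in constipated patients. Adverse effects also have their own sheet. The missing direction remains, and item II shows that the authors stated one elsewhere.

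**Main outcome and item II.** The Bristol and covariate points do not touch them. They do share the timing gap: the main outcome names no visit, and item II does not say which 15 days are averaged.

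**Conclusion.** The point holds as a specification gap in the secondary analyses, worth correcting before data are analyzed. For butyrate, microbiota, glucose and HbA1c the plan leaves open which between-arm result decides, whether baseline is adjusted for, and the visit. On the assumed effect and correlations, baseline-adjusted ANCOVA gains about 3 to 20 points of power over unadjusted follow-up values, and about 19, 10 and 3 points over change scores at r = 0.3, 0.5 and 0.7. These sizes rest on assumed inputs; the gap in the text does not.

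The Bristol definition, as written, can score harder or watery stool as an effect. How often that would happen cannot be determined, because the meaning of the 50% is unclear.

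The documents do not support reading this as a defect in the test of the main outcome. For that outcome only the unnamed visit is at issue.

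**What to change.** **Continuous outcomes.** For each one with both a baseline and a follow-up measurement, make ANCOVA of the follow-up value the main between-arm analysis, with arm as factor and that outcome's own baseline as covariate. Section 8 schedules the SF-36 only at Visit 3, so the model cannot be applied to it as the schedule stands.

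**Timing.** Use Visit 5, or Visit 4 for SmartPill transit, its only post-baseline measurement. State which 15 diary days form baseline and follow-up for all diary outcomes, including the main outcome and item II. Only one week is fixed between Visits 2 and 3, so check that 15 baseline days will exist.

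**Reporting.** Give adjusted differences with 95% CIs for each agave arm against psyllium and, for secondary objective 1, for 5 g against 10 g. Fix the analysis scale of each outcome in advance. Label ANOVA/Kruskal-Wallis, percent change and other visits as supportive.

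**Bristol.** Analyze the 15-day mean score by the same model. Restate the response with a direction, an upper bound that does not count watery stool as benefit, and a denominator (score or share of stools). Specifying an upward change alone would still count watery stool.

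**Cost.** Wording only, since baseline blood, stool and diaries are already planned, subject to the check on baseline diary days. The downside is about 1 point of power if baseline does not predict follow-up, and slightly less comparability with papers that report percent change.

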- functional constipation ROME III criteria as
- Subjects ≥55 years with recent colonoscopy (<3 years)

b) Exclusion criteria

- Taking supplements of fiber in the last 2 months
- Stimulant laxatives consumption chronically (Senna, Bisacodyl)
- decompensated comorbidities (example: uncontrolled diabetes mellitus HbA1c > 9%, decompensated Organ failure, decompensated hypertension (untreated or TA > 160 mmHg systolic and 95 mmHg diastolic)

- Using digital maneuvers or enemas to achieve evacuation
- Personal history of active or previous cancer
- abdominal surgery (except appendectomy, cholecystectomy, hysterectomy)
- Presence of alarm data in the last 6 months (trans-rectal bleeding, unexplained weight loss, abdominal pain)
- Use of drugs known promote constipation (opioid derivatives, clacioantagonistas, anticholinergics tricyclic antidepressants type)
- Prostration (immobility or poor mobility)
- Diseases such as untreated hypothyroidism with hormone replacement, and diseases associated with hypercalcemia that promote constipation
- Other causes of secondary constipation
- Meet criteria for constipation predominant irritable bowel
- Pregnancy.

c) Elimination criteria (considering pregnancy if necessary).

- Requiring individuals to withdraw their informed consent
- acute illness (eg appendicitis, medical-surgical requiring hospitalization intervention and follow-up)
- In our study provides no substitute for patients who have completed or prematurely abandoned the study. It is contemplated an analysis by intention to treat and the percentage of losses for each treatment group will be collected, clarifying the reason why the study was abandoned.

10. Methodology: Outcomes and variables

a) Variables / Main outcome measure

b) Variables / secondary endpoints measured

b) frequency measurements,

c) Criteria for success and failure, and if necessary

d) Strategy statistical analysis.

Where applicable should be specified and substantiated techniques, equipment and / or instruments to be used in the measurement (this includes mechanical / electronic / cyber special equipment, evaluation forms, questionnaires, matching tables, etc.), indicating the validity criteria , reproducibility and quality controls that are the same.

main outcome variable:

Effect of supplementation of fructans Tequilana Weber blue agave in increasing at least one complete evacuation from basal spontaneous.

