The sample size was calculated from the formula mean differences for non-inferiority studies and data from 52 studies were used Holscher HD., Et a38, Erdogan A., et al 53 and R Closa-Monasterolo , et al 54. accuracy of 95% (0.05 probability of making an error or type I was used α) And a force or power of 80% (0.20 probability of committing a type II error or β).

$$n = \lambda/\Delta.$$

Where:

n = sample size

$$\lambda = 10.91$$

$$\Delta = 1$$

Where:

$$\Delta = \frac{1}{(\sqrt{\sum \sigma^2})} (\sum \sigma)$$

$$\sigma_1 = 0.01$$

$$\sigma_2 = 0.12$$

$$\sigma_3 = 0.43$$

$$\sigma_4 = 0.27$$

$$= \Delta \frac{1}{(0.82)} (0.82) = 1$$

$$= 10.91 \approx 11 n = 10.91/1$$

Taking a 20% loss during the study sample size are:

$$n = 13 \approx 15$$

d) Statistical significance

It is considered each of the variables under study as the statistically significant with a value of $p < 0.05$

e) Statistical analysis of the population

The study population are volunteers with functional constipation and statistically analyzed considering the per protocol population and intent-to treat.

f) statistical treatment

It does not, in our strategy of statistical analysis a power of 80% for our study with an alpha of 0.05 is contemplated to demonstrate non-inferiority. Therefore, a greater percentage of losses accepted 20% to give validity to our study.

11. List of materials to use resources.

Team	Model	Description
portable stadiometer	Seca213	Measuring range 20-205 cm Division 1 mm Brand: Seca
Impedance	RJLQIV	Impedance Analyzer Brand: RJL Systems Includes: analyzer, charger case, LEMO cables, resistor, 400 electrodes, software
Weighing machine	BBZ-420	Maximum capacity up to 140 Kg minimum division 100 g Zamac bar with matt chrome Pylons cursors zamac beige or white enameled Base 54 x 20 x 10.5 cm Scale weight: 17 kg authorization NOM Made from sheet metal Finished in baked enamel paint

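### The sample-size step divides 0.82 by itself and no non-inferiority margin is stated, so 80% power with 15 per arm is not established

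*Combined protocol and SAP*

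**What the plan says.** The relevant text is in section 10 of the combined protocol and SAP, under Data analysis.

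- **c) Sample size:** "The sample size was calculated from the formula mean differences for non-inferiority studies". The error rates are given as "0.05 probability of making an error or type I was used" and "power of 80% (0.20 probability of committing a type II error or β". The rule is n = λ/Δ with λ = 10.91. Δ is displayed as the sum of four σ values divided by a square root involving their squares, and the σ are 0.01, 0.12, 0.43 and 0.27. The worked line is then one over 0.82, times 0.82, equal to 1. This gives n = 10.91, rounded to 11, and 13 raised to 15 after a 20% loss.
- **f) Statistical treatment:** "a power of 80% for our study with an alpha of 0.05 is contemplated to demonstrate non-inferiority". The start of that sentence is garbled in translation.
- **b) Non-inferiority study:** the aim is to "generate clinical evidence and demonstrate the therapeutic potential similar to plantago psyllium". No margin follows.
- **a) Statistical analysis plan:** "For comparison between groups ANOVA (variables with normal distribution) or Kruskal-Wallis (non-normal distribution variables) used for continuous variables".
- **Main outcome variable:** the effect of agave "in increasing at least one complete evacuation from basal spontaneous". Whether this is analysed as a mean change or as a proportion of responders is not said.

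Section 8 plans 60 patients, 15 in each of four arms. It also notes that earlier fibre-supplement studies used 25 to 30 per group to find differences.

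**The concern.** A non-inferiority sample size needs a margin, an expected difference and a measure of variability on the scale of the primary outcome. None of these can be identified here. The only step that could carry them into the calculation is Δ, and Δ is a number divided by itself. The plan's text does not say which outcome, unit or arm the four σ belong to, and it does not call any of them a margin.

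Without a margin there is no criterion for success on the question the trial is meant to answer. A reader who sees no significant difference between agave and psyllium could not tell whether that supports non-inferiority or only reflects small arms. The printed 80% invites the first reading.

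**Working it through.** **1. The plan's own figure.** Inputs from c): λ = 10.91 and Δ = (1/0.82) × 0.82 = 1.

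n = 10.91/1 = 10.91, rounded to 11. For 20% loss, 11 × 1.2 = 13.2 and 11/0.8 = 13.75. The stated 13, raised to 15, is acceptable from that point on. The final steps reproduce, but only once Δ = 1 is taken as given.

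**2. Does Δ = 1 follow from the listed σ?**

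- Σσ = 0.01 + 0.12 + 0.43 + 0.27 = 0.83 (the worked line has 0.82).
- Σσ² = 0.0001 + 0.0144 + 0.1849 + 0.0729 = 0.2723, so √Σσ² = 0.522 (the worked line again has 0.82).
- Formula as displayed: Δ = 0.83/0.522 = 1.59, and n = 10.91/1.59 = 6.9.

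The display may have been damaged in translation or extraction, so the 6.9 is conditional on it. The point rests on the worked line, which is legible.

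**3. Where λ = 10.91 could come from.** The plan does not say. The noncentrality that gives 80% power at alpha 0.05 for a chi-square test with 3 degrees of freedom is 10.90; with 1 degree of freedom it is 7.85. So λ matches an overall test that four group means are equal. This is an inference, but it agrees with the ANOVA or Kruskal-Wallis test named in a). Such a test looks for any difference among four arms.

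**4. What 15 per arm can deliver on a continuous scale.** Assumptions: one agave arm against psyllium, no true difference, normal approximation, margin in SD units. The plan does not state sidedness for the non-inferiority test, so both levels are shown.

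Margin at 80% power = (z + 0.8416) × √(2/n), with z = 1.645 or 1.960. The 12 per arm is 15 × 0.8.

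| n per arm | one-sided 0.05 | one-sided 0.025 |
|---|---|---|
| 15 | 0.91 SD | 1.02 SD |
| 12 | 1.02 SD | 1.14 SD |

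Power with 15 per arm = Φ(m/√(2/15) − z):

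| Assumed margin m | one-sided 0.05 | one-sided 0.025 |
|---|---|---|
| 0.25 SD | 17% | 10% |
| 0.50 SD | 39% | 28% |
| 0.75 SD | 66% | 54% |
| 1.00 SD | 86% | 78% |

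**5. The same on a responder scale (an assumption).** The only response figure available is the 57% average for psyllium in section 6, Treatments. It is an undefined response in other studies, so it serves only as an illustration.

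Margin at 80% power = (z + 0.8416) × √(2 × 0.57 × 0.43/n):

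- 15 per arm: 45 points (one-sided 0.05) or 51 points (one-sided 0.025).
- 12 per arm: 50 or 57 points.

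For common response rates from 40% to 70%, the range over both levels is 42 to 51 points with 15 per arm and about 47 to 57 with 12.

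**6. Expected precision of agave minus psyllium (95% CI half-width).**

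- Continuous: 1.96 × √(2/15) = ±0.72 SD; with 12 per arm, ±0.80 SD.
- Binary at 57%: 1.96 × √(2 × 0.57 × 0.43/15) = ±35 points; with 12 per arm, ±40 points.

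**The case against.** The strongest objection concerns the recomputed Δ. If the display originally showed the root of the squared sum, the denominator would equal the numerator and Δ would be exactly 1, as worked. The gap between 0.83 and 0.82 could be rounding of four two-decimal inputs. That is fair, and it is why the 6.9 should not carry weight. It does not rescue the calculation: under that reading Δ is 1 for any σ at all, so n still depends only on λ.

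The margins in the working also depend on their assumptions. The hypothesis in section 7A allows agave to be better. With a true advantage of 0.25 SD the 80%-power margin at 15 per arm falls to 0.66 or 0.77 SD. Pooling the agave arms (45 against 15) would bring it to 0.74 or 0.84 SD, but the plan does not describe pooling. In the other direction, t-based calculation raises the margins to 0.93 or 1.06 SD with 15 per arm and widens the half-widths to ±0.75 SD (±0.85 SD with 12). The 12-per-arm figures assume that lost patients leave the analysis, whereas the plan also names intention to treat. None of these variants supplies the missing margin.

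The σ values may be defined in the studies the plan cites, which were not available here. What can be said is that the plan's own text does not define them. Section f) is poorly translated and weak support by itself, but c) states both 80% power and non-inferiority plainly.

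**Conclusion.** The concern holds. The worked line makes n equal to λ, no variability or effect assumption enters the sample size, and no margin appears in any section. The one-evacuation threshold in the main outcome is a change from baseline, not a between-arm margin, and Δ = 1 is a ratio of σ values. The 80% power for non-inferiority is therefore not established for 15 per arm.

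This does not show that 15 per arm is too few for every margin. Under equal true means and pairwise comparison, it reaches 80% at a margin of about 0.9 to 1.0 SD, or about 1.0 to 1.1 SD with 12 completers. If the outcome is a proportion near 57%, the margin would be about 45 to 51 points with 15 per arm. The plan offers no justification for margins of that size. Confidence is high. The point needs correcting because the planned demonstration of similarity to psyllium has no success criterion as written.

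**What to change.** - In c), delete the Δ = 1 derivation. In f), delete the statement of 80% power for non-inferiority.
- State whether the main outcome is analysed as a mean change or as a proportion.
- State what 15 per arm (about 12 after 20% loss) delivers for each agave-minus-psyllium difference. By normal approximation the expected 95% CI half-width is about ±0.72 SD (±0.80 SD with 12) if continuous, or about ±35 points (±40 with 12) if binary at an assumed 57%. The t-based ±0.75 and ±0.85 SD are slightly more cautious for the continuous case.
- Add a non-inferiority margin that the sponsor states and justifies, the one-sided alpha, and the power at that margin. Add one line to a) naming the confidence interval to be set against it.
- Unless that power is adequate, do not call the psyllium comparison a non-inferiority test with 80% power. Report it as an estimate with its confidence interval.

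The cost is a rewrite of two short paragraphs and one added line. The stated power may become less favourable. The correction itself needs no extra patients.
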